6.2. Concomitant Therapy

Both experimental group and control group will receive systemic steroid with/without intratympanic steroid as the standard treatment for sudden sensorineural hearing loss.

Hyperbaric oxygen therapy, a common therapy for sudden sensorineural hearing loss, is also allowed in these patients.

7. Efficacy Assessments

The evaluation of hearing ability is performed by pure tone audiometry, speech audiometry and word recognition test(WRS).

The audiometry will be arranged during the first clinic visit and followed at day 56 and day 84. Then the differences of the pre- and posttreatment audiometry will be evaluated.

The pure-tone average(PTA) calculated using 0.5-, 1-, 2-, and 3-kHz air conduction thresholds. The WRS is presented as percentage. The treatment efficacy compares the difference of PTA and WRS before and after treatment.

8. Safety Assessments

The most frequent side effects of the study drug are mild disturbance in taste, appetite, and paresthesia of distal extremities. There are no major adverse events reported in previous clinical trials. Those symptoms will be monitored and recorded during each clinical follow-up (from the first clinic to the end of follow-up after 3 months).

9. Adverse event reporting

[name] will report SAEs to the IRB of Chang Gung Medical Foundation according to the Serious Adverse Event Reporting Procedures and Guidelines as posted in the Clinical Trials Resource on the website of Chang Gung Medical Foundation IRB. SAE reports to the IRB should include the following information when calling the Medical Monitor:

- Date and time of the SAE
- Date and time of the SAE report
- Name of reporter
- Call back phone number
- Affiliation/Institution conducting the study
- Protocol number

- Title of protocol
- Description of the SAE, including attribution to drug and expectedness

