5.2 Exclusion Criteria

Exclusion criteria:

- (1) Previous SSNHL history
- (2) Previous middle ear disorder such as chronic otitis media, or previous ear surgery
- (3) Meniere's disease and fluctuating hearing loss patients
- (4) Pregnancy or trying to become pregnant
- (5) Leukemia, hemodialysis, and patients who received chemotherapy before.
- (6) Previous head and neck radiotherapy
- (7) CP angle tumor such as vestibular schwannoma
- (8) Patients with moderate to severe hepatic insufficiency
- (9) Patients with major depression disorder or suicide attempt
- (10) Patients with glaucoma

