9.1 Definitions and reports of Adverse Events

All adverse events that occur after the informed consent is signed (including run-in) must be recorded on the adverse event CRF (paper and/or electronic) whether or not related to study agent. AE Data Elements including:

- AE reported date
- AE Verbatim Term
- CTCAE Term (v 5.0)
- Event onset date and event ended date
- Severity grade
- Attribution to study agent (relatedness)
- Whether or not the event was reported as a Serious Adverse Event (SAE)
- Action taken with the study agent
- Outcome of the event
- Comments

Identify the adverse event using the NCI Common Terminology Criteria for Adverse Events (CTCAE) version 5.0. The CTCAE provides descriptive terminology and a grading scale for each adverse event listed.

AEs will be assessed according to the CTCAE grade associated with the AE term. AEs that do not have a corresponding CTCAE term will be assessed according to their impact on the participant's ability to perform daily activities as follows:

Grade	Severity	Description
1	Mild	
• Barely noticeable, does not influence functioning• Causing no limitations of usual activities
2	Moderate	
• Makes participant uncomfortable, influences functioning• Causing some limitations of usual activities
3	Severe	
• Severe discomfort, treatment needed• Severe and undesirable, causing inability to carry out usual activities
4	Life threatening	
• Immediate risk of death• Life threatening or disabling
5	Fatal	
• Causes death of the participant

The possibility that the adverse event is related to study drug will be classified as one of the following: not related, unlikely, possible, probable, definite.

DEFINITION of Serious Adverse Events: ICH Guideline E2A and GCP of Taiwan define serious adverse events as those events, occurring at any dose, which meet any of the following criteria:

- Results in death

- Is life threatening (Note: the term life-threatening refers to an event in which the patient was at risk of death at the time of the event; it does not refer to an event which hypothetically might have caused death if it were more severe).
- Requires inpatient hospitalization or prolongation of existing hospitalization
- Results in persistent or significant disability/incapacity
- Is a congenital abnormality/birth defect

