11.2.2 Safety analysis

The medication used in this study is well studied in the previous clinical trials. The possible adverse effects of the medication will be monitored during each follow-up. The adverse effects of the medication will be analyzed at the end of study.

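### Section 8 monitors three mild symptoms while 9.1 requires all adverse events; the safety scope, last safety visit and attribution wording in 11.2.2 need reconciling

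*Protocol*

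**What the plan says.** Protocol Section 8 (Safety Assessments) opens with "The most frequent side effects of the study drug are mild disturbance in taste, appetite, and paresthesia of distal extremities". It continues: "There are no major adverse events reported in previous clinical trials. Those symptoms will be monitored and recorded during each clinical follow-up". It gives the period as running from the first visit until follow-up ends at 3 months.

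Other sections describe the same task differently:

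- Section 9.1: "All adverse events that occur after the informed consent is signed (including run-in) must be recorded on the adverse event CRF", related or not, with CTCAE term, grade, attribution and a flag for seriousness. Sections 9 and 9.2 add reporting to the IRB and follow-up of all events.
- Section 4.3: patients in both arms attend on days 7, 14, 21, 28, 56 and 84. Symptoms and adverse effects in general are followed at all of these except day 84.
- Section 2.4: the potential effects of topiramate are the same three symptoms plus a raised risk of fetal oral cleft.
- Section 5.2 excludes, among others, "Patients with major depression disorder or suicide attempt" and "Patients with glaucoma". No reason is given for either.
- Section 11.2.2: "The adverse effects of the medication will be analyzed at the end of study".
- Synopsis: the trial is open, with no blinding of patient or evaluator.

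**The concern.** Three things do not fit together.

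1. **Scope of ascertainment.** A site working from Section 8 would ask about three symptoms, whereas a site working from 9.1 would make a broader enquiry. With four hospitals and open treatment, the number and type of events found could depend on which section a site follows and on which arm the patient is in.
2. **Risk picture.** The statement about major events in earlier trials is the only justification offered near the short list, and it does not sit easily with Sections 2.4 and 5.2.
3. **Analysis set.** Section 9.1 collects all events, but 11.2.2 speaks of effects of the drug. Deciding what counts as an effect of the drug requires a judgement of cause, made here by people who know the allocation.

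At stake is how far any statement on the tolerability of topiramate added to steroid can be trusted. Both arms receive systemic steroid, so comparing all events by randomised arm is what separates the contribution of topiramate from that of background treatment. Section 10 also allows the trial to stop for harm, and that decision would draw on the same data.

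**Working it through.** The point concerns wording and timing, so the check sets the sections side by side. The only arithmetic is on visit days.

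**Scope**

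- Section 8: the monitored symptoms refer back to the list just given, which has three items, all described as mild and frequent.
- Section 9.1: all events after consent, regardless of relatedness.
- Section 4.3: symptoms and adverse effects, with no list. The table has a single row for symptoms and no items under it.
- Section 11.2.2, on monitoring: possible effects of the medication at each follow-up, again with no list.

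Section 8 is therefore the narrow one. It does not say that only those symptoms are followed, but it does not point to 9.1 either. It is framed around side effects of the study drug, which the control arm does not take, so it does not make clear that control patients are asked the same questions. Section 9.1 fixes what must be recorded, not how events are elicited.

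**Timing**

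- Post-baseline visits in Section 4.3: days 7, 14, 21, 28, 56, 84, which is 6 visits.
- Safety visits in Section 4.3: days 7, 14, 21, 28, 56, which is 5 visits.
- Section 8, every follow-up to 3 months: all 6.
- Difference: 6 − 5 = 1 visit (day 84), and 84 − 56 = 28 days.

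A related mismatch affects the same visits. The synopsis has weekly clinic visits to the sixth week, that is to day 6 × 7 = 42, but Section 4.3 lists none on days 35 or 42. Under Section 4.3 the last visit during the six-week treatment period is day 28, which leaves 42 − 28 = 14 days of treatment without a scheduled contact.

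**Risk picture**

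Section 2.4 names four potential effects and Section 8 carries over three; the fetal risk is missing. Section 5.2 removes patients with major depression or a suicide attempt and patients with glaucoma. None of these conditions concerns hearing, so a link to treatment safety is a reasonable inference. The protocol does not state it, and because both arms take systemic steroid the text does not tie the exclusions to topiramate.

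**Analysis**

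Section 9.1 records each event with an attribution on a five-level scale from not related to definite. Under open treatment that grade is assigned with the arm known. If the wording of 11.2.2 is taken to mean attributed events, the analysed set is a subset of what 9.1 collects, selected by an unblinded judgement. Section 11.2 plans chi-square tests for categorical variables between groups, so an all-event comparison by arm is possible, but 11.2.2 does not commit to it.

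**The case against.** The strongest defence is that the protocol already has a full safety system. Section 4.3 schedules general safety follow-up for patients attending in both arms. Sections 9 to 9.2 require every event to be recorded, graded, followed up and, if serious, reported, and they extend reporting to events that look unusual or potentially serious. On this view Section 8 merely has a loose pronoun, and the layout of adverse event tables belongs in a statistical analysis plan that is not at hand.

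Much of this stands, and it rules out several stronger readings:

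- A reader might infer that serious effects are not looked for. The documents do not support that: Sections 4.3 and 9 to 9.2 would capture a serious event once reported or noticed.
- A reader might infer that control patients cannot contribute events to the analysis. That is only one reading of 11.2.2. Events are recorded regardless of relatedness, and the text does not expressly restrict the analysis to attributed events.
- A reader might take the exclusions as proof of known topiramate risks. The protocol gives no reason for them.
- A reader might call the sentence on major events false. It speaks of what earlier trials reported, not of what is known, and those trials cannot be examined here.

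The defence does not remove the conflicts in the text. Sections 8 and 9.1 differ in scope, and Sections 8 and 4.3 differ in the last safety visit. Table layout can be left to an analysis plan. The wording of 11.2.2 is different: the protocol itself describes the analysed events more narrowly than the events it collects.

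**Conclusion.** The point holds as an inconsistency that should be corrected, not as a failure of safety reporting. Section 8 is narrower than 9.1 in what is monitored, and its follow-up runs 28 days past the last safety visit in Section 4.3. Its reassurance fits poorly with Sections 2.4 and 5.2. As written, events beyond the three symptoms are not clearly sought in a uniform way across arms and sites, and 11.2.2 invites an attribution-based analysis that leaves the randomised comparison unused.

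This rests on reading Section 8 literally and on the open design stated in the synopsis. How many events would be missed cannot be derived from the protocol. A bound on event rates from the size of the topiramate arm would reflect the sample size rather than this wording, so none is given. The general recording duty in 9.1 keeps the matter from being more serious.

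**What to change.** - Reconcile Section 8 with Sections 9.1, 2.4, 5.2 and 4.3, in both the scope of events and the last safety visit, and bring the synopsis visit pattern into line. The sponsor decides which schedule is intended.
- State that the same enquiry, covering all adverse events, is made in both arms and at all sites at each scheduled safety visit. Whether the conditions behind the depression/suicide and glaucoma exclusions are asked about specifically is for the sponsor to decide and state.
- Reword the statement on major adverse events so that it is consistent with Sections 2.4 and 5.2, or give its basis.
- Change 11.2.2 to tabulate all adverse events and serious adverse events by randomised arm regardless of attribution, with drug-attributed events as a secondary listing.

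The cost is text edits and one revised table, using data that 9.1 already requires. Patients already attend on both day 56 and day 84, so settling the choice between those two end points adds no visit; restoring the synopsis's weekly pattern would. The downside is slightly more reported events.

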9.1 Definitions and reports of Adverse Events

All adverse events that occur after the informed consent is signed (including run-in) must be recorded on the adverse event CRF (paper and/or electronic) whether or not related to study agent. AE Data Elements including:

- AE reported date
- AE Verbatim Term
- CTCAE Term (v 5.0)
- Event onset date and event ended date
- Severity grade
- Attribution to study agent (relatedness)
- Whether or not the event was reported as a Serious Adverse Event (SAE)
- Action taken with the study agent
- Outcome of the event
- Comments

Identify the adverse event using the NCI Common Terminology Criteria for Adverse Events (CTCAE) version 5.0. The CTCAE provides descriptive terminology and a grading scale for each adverse event listed.

AEs will be assessed according to the CTCAE grade associated with the AE term. AEs that do not have a corresponding CTCAE term will be assessed according to their impact on the participant's ability to perform daily activities as follows:

Grade	Severity	Description
1	Mild	
• Barely noticeable, does not influence functioning• Causing no limitations of usual activities
2	Moderate	
• Makes participant uncomfortable, influences functioning• Causing some limitations of usual activities
3	Severe	
• Severe discomfort, treatment needed• Severe and undesirable, causing inability to carry out usual activities
4	Life threatening	
• Immediate risk of death• Life threatening or disabling
5	Fatal	
• Causes death of the participant

The possibility that the adverse event is related to study drug will be classified as one of the following: not related, unlikely, possible, probable, definite.

DEFINITION of Serious Adverse Events: ICH Guideline E2A and GCP of Taiwan define serious adverse events as those events, occurring at any dose, which meet any of the following criteria:

- Results in death

- Is life threatening (Note: the term life-threatening refers to an event in which the patient was at risk of death at the time of the event; it does not refer to an event which hypothetically might have caused death if it were more severe).
- Requires inpatient hospitalization or prolongation of existing hospitalization
- Results in persistent or significant disability/incapacity
- Is a congenital abnormality/birth defect
- Events that may not meet these criteria, but which the investigator finds very unusual and/or potentially serious, will also be reported in the same manner.

9.2 Adverse event follow-up

All AEs, including lab abnormalities that in the opinion of the investigator are clinically significant, will be followed according to good medical practices and documented as such. Site staff should send follow-up reports as requested when additional information is available. Additional information should be entered on the IRB of Chang Gung Medical Foundation of SAE form in the appropriate format. Follow-up information should be sent to Chang Gung Medical Foundation IRB as soon as possible according to IRB's Serious Adverse Event Reporting Procedures and Guidelines.

10. Criteria for the termination of the trial

The trial can be ended before the planned end date because of evidence of adverse effects (harm), or likelihood of failing to reject the null hypothesis (futility)

11. Statistical Considerations

t test will be performed to compare pre- and posttreatment audiometric measurements. Chi-square and independent sample t test will be used to compare categorical and numerical variables between the two groups, respectively.

11.1 Sample size Determination

The study will be powered to approximately 80% assuming a standard deviation of 13 at an alpha of 0.05. The number of patients required to observe a 5dB difference between the experimental group and control group is about 56 patients in each group if the superiority margin at 0.05. The total estimated patients number required is 112. Consider the patient with incomplete data and drop-out rate of 20%, the total estimated number of sample size is about 140.

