0.80	0.80630	56	56	112	12.0	19.0	-7.0	13.0	0.050

References

Julious, S. A. 2010. Sample Sizes for Clinical Trials. Chapman & Hall/CRC. Boca Raton, FL.
Chow, S. C., Shao, J., and Wang, H. 2008. Sample Size Calculations in Clinical Research (Second Edition). Chapman & Hall/CRC. Boca Raton, FL.
Zar, Jerrold H. 1984. Biostatistical Analysis (Second Edition). Prentice-Hall. Englewood Cliffs, New Jersey.

Report Definitions

Target Power is the desired power value (or values) entered in the procedure. Power is the probability of rejecting a false null hypothesis.

Actual Power is the power obtained in this scenario. Because N1 and N2 are discrete, this value is often (slightly) larger than the target power.

N1 and N2 are the number of items sampled from each population.

N is the total sample size, $N1 + N2$.

μ_1 and μ_2 are the assumed population means.

$\delta = \mu_1 - \mu_2$ is the difference between population means at which power and sample size calculations are made.

σ is the assumed population standard deviation for each of the two groups.

Alpha is the probability of rejecting a true null hypothesis.

Summary Statements

Group sample sizes of 56 and 56 achieve 80.630% power to reject the null hypothesis of equal means when the population mean difference is $\mu_1 - \mu_2 = 12.0 - 19.0 = -7.0$ with a standard deviation for both groups of 13.0 and with a significance level (alpha) of 0.050 using a two-sided two-sample equal-variance t-test.

*Missing rate =10%, thus the enrollment size is 112/0.9=125

*Missing rate =20%, thus the enrollment size is 112/0.8=140

3. Efficacy assessment group : V Intent-to-treat (ITT) Per-Protocol (PP)
 Other _____
4. Interim analysis : Yes V No
5. Statistical methods : t test will be performed to compare pre- and posttreatment audiometric measurements. Chi-square and independent sample t test will be used to compare categorical and numerical variables between the two groups, respectively.
6. Handling of Missing Data : The cases with missing data will be omitted. The remaining data will be analyzed to determine the efficacy of study drug.

2. Introduction and Rationale

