4.2 Number of Patients

Enrolled number : **140**

Failed during screening : **10**

Drop-out number : **28**

Estimated evaluable number : **112** (experimental group 56, control group 56)

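### Section 11.1 claims about 80% power for a 5 dB difference with 56 per group, but the 56 was calculated for 7 dB; power at 5 dB is about 52%

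*Protocol*

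**What the plan says.** Two places in the protocol justify the sample size.

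- **Section 11.1 (Sample size Determination).** It opens with "The study will be powered to approximately 80% assuming a standard deviation of 13 at an alpha of 0.05" and continues "The number of patients required to observe a 5dB difference between the experimental group and control group is about 56 patients in each group", with the added condition "if the superiority margin at 0.05". It then goes from 112 evaluable to about 140 enrolled, allowing for 20% loss.
- **Synopsis, Statistical Methods (PASS output).** The alternative hypothesis is a non-zero difference in means. The summary sentence reads "Group sample sizes of 56 and 56 achieve 80.630% power to reject the null hypothesis of equal means" and gives the assumed difference as "12.0 - 19.0 = -7.0$ with a standard deviation for both groups of 13.0 and with a significance level (alpha) of 0.050". The test is stated "with a significance level (alpha) of 0.050 using a two-sided two-sample equal-variance t-test". The enrolment figure is again 112/0.8 = 140.

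Section 4.2 repeats the split ("experimental group 56, control group 56") and the total of 140. The standard deviation, alpha, power, group size, evaluable total and enrolled total all agree between the two places. The difference to be detected does not: 5 dB in one, 7 in the other. Nothing in the protocol reconciles them.

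**The concern.** With the other inputs fixed, 56 per group cannot be the 80% power sample size for both 5 dB and 7 dB. One of the two statements must be wrong.

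Section 11.1 is the formal sample-size section, so it is where an ethics committee, a reader of the results or a meta-analyst would look for the effect the trial can detect. If 5 dB is the difference of interest, the trial has roughly an even chance of missing it. A non-significant result could then be taken as evidence against a 5 dB benefit from an adequately powered trial. Section 10 also allows early termination for futility. A futility judgement usually leans on the assumed effect, and the protocol currently has two.

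The margin wording adds to the confusion. A superiority margin would be a value in dB by which the mean difference must exceed zero, and the Synopsis calculation has none.

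**Working it through.** **Inputs**

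- Standard deviation σ = 13 (Synopsis and section 11.1).
- Two-sided α = 0.05, two-sample equal-variance t test (Synopsis).
- n = 56 per group (Synopsis, sections 4.2 and 11.1).
- Difference δ = 7 (Synopsis) or 5 dB (section 11.1).
- Loss of 20% (Synopsis and section 11.1).

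**Formula.** Power comes from the noncentral t distribution with 2n − 2 = 110 degrees of freedom and noncentrality λ = δ / (σ√(2/n)). The standard error of the difference is 13 × √(2/56) = 2.457.

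**Step 1: reproduce the plan's own figure (7 dB).** λ = 7/2.457 = 2.85, and power = 0.8063. This matches the 80.630% in the Synopsis. With 55 per group power is 0.7991, so 56 is exactly the 7 dB answer.

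**Step 2: the same calculation at 5 dB.** λ = 5/2.457 = 2.04, and power = 0.5229. The normal approximation gives 0.530.

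**Step 3: sample size for 80% power at 5 dB.** The exact calculation gives 108 per group (107 gives 0.7997). That is 2 × 108 = 216 evaluable and 216/0.8 = 270 enrolled, or 270 − 140 = 130 more than planned.

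**Step 4: what 56 per group can detect.** The smallest difference with 80% power is 6.94 dB.

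**Step 5: could another reading make 5 dB work?**

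| Reading at 5 dB, SD 13 unless stated | Power | Per group for 80% |
|---|---|---|
| Two-sided 0.05, 56 per group | 52.3% | 108 |
| One-sided 0.05, 56 per group | 64.7% | 85 |
| Margin of 0.05 dB, one-sided 0.025, 56 per group | 51.5% | – |
| Margin of 0.05 dB, one-sided 0.05, 56 per group | 64.0% | – |
| All 140 evaluable (70 per group), two-sided 0.05 | 61.8% | 108 |

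For 56 per group to give 80% power at 5 dB, the standard deviation would have to be about 9.36, and both places state 13. A covariate-adjusted analysis could lower the effective standard deviation: a correlation of 0.7 gives 13 × √(1 − 0.49) = 9.28 and power of 80.6%. However, the planned between-group comparison is an unadjusted independent-sample t test, and no such correlation is assumed.

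**Step 6: the loss adjustment.** 112/0.8 = 140, which is correct.

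**The case against.** The best defence is that the 5 dB is a slip in one sentence. The Synopsis carries a complete calculation dated 2 August 2022, ten days before the date of protocol version 6. It gives means, standard deviation, sidedness, test and power, and it reproduces. On that view the design delivers the power it was calculated for, and a reader of the Synopsis is not misled. This is plausible, and it is why a correction of wording can suffice. It does not make section 11.1 right, because that section still attaches about 80% power to 5 dB.

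A second defence is that to observe 5 dB means the smallest observed difference that would reach significance. That value is 1.982 × 2.457 = 4.87 dB, close to 5. But the sentence gives the number of patients required and directly follows the 80% power statement, so it describes a power calculation.

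Three cautions stand:

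- The protocol gives no minimum important difference and no justification for 12 versus 19, so it does not itself settle which target is intended. Keeping 140 is sufficient only if the target is 7 dB.
- The PASS output labels the means only μ1 and μ2. Reading them as mean pure-tone gain in dB is an inference from the primary endpoint and from the unit in section 11.1. It is a natural one, but the sponsor should confirm it.
- That the margin of 0.05 is a mislabelled alpha is also an inference, since alpha already appears separately in the same section. Whatever its origin, it plays no part in a test of a zero difference, and as a margin in dB it barely changes power.

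**Conclusion.** The concern holds. Section 11.1 states a power that the design does not deliver for the difference it names: 52.3% rather than about 80% at 5 dB, a shortfall of about 28 percentage points. The chance of missing a true 5 dB difference is 47.7%. The 56 per group belongs to a 7 dB difference, for which the Synopsis figure of 80.63% is correct.

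The result rests on the protocol's own inputs: standard deviation 13, two-sided alpha 0.05, equal groups of 56 and an unadjusted two-sample t test. None of the alternative readings at the stated standard deviation gets above 65% power at 5 dB. The contradiction must be corrected before the protocol's power statement can be relied on.

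**What to change.** Rewrite section 11.1 to agree with the calculation in the Synopsis, for example:

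> Fifty-six evaluable patients per group give 80.6% power to detect a 7 dB difference in mean PTA gain (12 versus 19 dB), assuming a standard deviation of 13 dB, with a two-sided two-sample t test at alpha 0.05. Power for a 5 dB difference is about 52%.

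Delete the reference to a superiority margin of 0.05. The sponsor should confirm that 12 and 19 are mean PTA gains in dB.

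**Cost.** Protocol wording only. The stated detectable difference becomes less favourable, while the evaluable number stays at 112 and enrolment at 140, with no extra patients.

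If the sponsor instead decides that 5 dB is the target, the wording change only discloses the shortfall. The size would then have to be recalculated: 108 per group and 270 enrolled with the other inputs unchanged.
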